3.2.5.5 Additional Analyses of the Other Endpoint

Not applicable.

3.2.5.6 Subgroup Analyses

Not applicable.

3.2.6 CCI

3.2.6.1 Definition

Definition of CCI Endpoint 2
Primary analysis population
Benralizumab 30 mg, 3 doses, once every 4 weeks (at baseline [V1], Week 4 [V2] and Week 8 [V3])
s: Participant withdrawal, IPD, use of prohibited medicines/substances, asthma exacerbation (participants with exacerbations will be excluded from the primary analysis set)
 Graphical summary (boxplots) Descriptive statistics (mean, SD, median, minimum, and maximum) Spearman's rank correlation coefficient Regression coefficients (95% CI)

3.2.6.2 Derivations

CCI participants will be categorized as follows:

1 Participants with any improvement in total score at Week 13 will be the participants with a total score at Week 13 lower than the total score at baseline.

- 3 Participants showing CCI
- 4 **CCI**

CCI subgroups of participants will be created as follows (Juniper et al., 2005; Juniper at al 2006):

1	CCI	CCI	CCI
	CCI		
2	CCI		

ccl subgroups of participants will be created as follows:

will be the participants with a total score at Week 13 at least 4 points lower than the total score at baseline.

3.2.6.3 Handling of Dropouts and Missing Data

Participants withdrawing before Week 13 and participants with one of the two measurements missing will not be included in the analysis.

3.2.6.4 Primary Analysis of Tertiary Endpoint 2

Participants will complete two versions of the CCI

(at Visit 4 (Week 13)). The first seven impairment items are evaluated over the past 2 weeks and the last three risk items over the past year for CCI

Change from baseline at Week 13 in each imaging endpoint (including: all FRI parameters in Table 2) will be summarized numerically (mean, SD, median, minimum, and maximum) and graphically (using a boxplot), for four CCI subgroups of participants: CCI

Change from baseline in each imaging endpoint will also be summarized for two CCI

CCI

CCI

CCI

For CCI	the change from baseline in each imaging endpoint will	be summarized for
those achiev	ving a CCI	

Three adjusted and unadjusted models of the form described in Section 3.2.4.4 will be fitted for each imaging endpoint, where the covariate x_2 is **CC**

separate models will also be estimated with the response to items 2, 4, and 8 and their pairwise interactions as covariates.

Estimated regression coefficients for time, β_1 , from the unadjusted and adjusted models will be reported with 95% CIs and p-values, and compared to indicate whether the change from baseline in the imaging parameter is explained by changes from baseline in **CC**

. Estimated regression coefficients, CCI

CCI will be reported with 95% CIs and p-values, to quantify how changes in **CCI** impact on the change from baseline in each imaging endpoint.

Scatterplots will be used to visualize associations between changes from baseline in imaging parameters and questionnaire scores.

3.2.6.5 Additional Analyses of the Tertiary Endpoint 2

Not applicable.

3.2.6.6 Subgroup Analyses

Subgroups are described in Section 3.2.6.4.

3.2.7.1 Definition

Table 10	Definition of CC Endpoint 3
Population:	
Endpoint:	
Treatment:	
Intercurrent events	
Population-level summary:	

3.2.7.2 Derivations

CCI		
_	CCI	l
CCI		

3.2.7.3 Handling of Dropouts and Missing Data

Participants withdrawing before Week 13 and participants with one of the two measurements missing will not be included in the analysis.

3.2.7.4 Primary Analysis of CCI Endpoint 3

The mean change from baseline (Week 0 to 13) in CCI for a CCI

or a CCI

) will be calculated, without adjustment for participant characteristics. A paired t-test will be used to evaluate the

statistical significance of the difference in means at Week 0 versus Week 13. The level of significance will be taken to be 0.05.

3.2.7.5 Additional Analyses of the Tertiary Endpoint 3

Not applicable.

3.2.7.6 Subgroup Analyses

Not applicable.

3.3 Pharmacodynamic Endpoint(s)

Not applicable.

3.3.1 Analysis

Not applicable.

3.3.2 Definitions and Derivations

Not applicable.

3.3.3 Presentation

Not applicable.

3.4 Pharmacokinetics

Not applicable.

3.5 Immunogenicity

Not applicable

3.6 Safety Analyses

All safety variables will be summarized using the safety analysis set and data presented according to actual treatment received.

Safety data will be presented using descriptive statistics unless otherwise specified.

All safety measurements will use all available data for analyses, including data from unscheduled visits and repeated measurements.

The domain safety covers exposure, Adverse events (AEs), clinical laboratory, vital signs, and ECG results.

Tables and listings are provided for the safety set.

3.6.1 Exposure

3.6.1.1 Definitions and Derivations

There are only 3 planned study intervention administrations. Study intervention exposure will be reported as the number of treatments effectively administered. This will be three for participants that correctly complete the treatment. In case of any interruption, the actual number of treatment administrations will be reported.

3.6.1.2 Presentation

Treatment exposure will be summarized in the safety analysis set as the number and percentage of participants that were administered with 3, 2, 1 study intervention administrations.

A by-participant listing of study intervention administration data will be provided. Dates and times will be listed for each participant and treatment administration.

3.6.2 Adverse Events

3.6.2.1 Definitions and Derivations

AEs are collected from the time of first dose of IP, throughout the treatment period and until Week 15 safety follow-up period is completed. AE causality is as determined by the reporting investigator. AEs with date of onset on or after the earliest first dose of any of the components of the combination should be considered to be treatment emergent.

AEs will be coded using the most recent version of MedDRA that will have been released for execution by the Sponsor/designee.

Multiple occurrences of an AE in the same participant will only be counted once overall considering start date as the first day of first occurrence and stop date the last day of the last occurrence.

In the case that, during the study, a participant has more than one episode of the same preferred term with different levels of intensity, then the maximum intensity level will be used. The following ordering will be used to define maximum intensity level: Mild < Moderate < Severe.

For each participant and each AE, the worst severity recorded will be attributed and used in the by-severity summaries. Similarly, the worst causality (most related to study intervention) will be attributed and used in the by-causality summaries. If severity or causality is missing, a conservative approach for AE assessment (taking into account the worst case) will be followed.

Any AEs with incomplete start and end dates/times will be treated as follows:

- AEs with unknown start times, but with start date known, will be imputed with a time of 00:00, unless the start date corresponds to any given dosing date. In this case the start time will be imputed with the time of dosing. If this results in a start date/time after end date/time of the AE, then the time will also be imputed with 00:00.
- AEs with completely unknown start dates will be imputed with the date and time of dosing unless the end date is known and prior to dosing; in that case the start date will be imputed as the date of screening and a time of 00:00.
- AEs with partially known start dates/times will be treated as follows:

- If only the day is missing, then the day will be imputed with the first day of the month, unless the month and year in which the AE started is a month and year in which study intervention was administered, then the day will be imputed with the first day on which study intervention was administered in that month. If this results in a start date after the end date, then the day will be imputed with the first day of the month.
- If only the month is missing and the year is a year in which study intervention was administered, then the month will be imputed with the first month in which study intervention was administered. If this results in a start date after the end date of the AE, then the month will be imputed with JAN. If the known year part is not a year in which study intervention was administered, then the month will also be imputed with JAN.
- If both the day and month is missing and the year is a year in which study intervention was administered, then the day and month will be imputed with the day and month of dosing. If this results in a start date after end date, then the day and month will be imputed with 01JAN. If the year is not a year in which study intervention was administered, then the day and month will also be imputed with 01JAN.
- If only the year is missing, then the year will be imputed with the year of dosing.

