8.4.1 Time Period and Frequency for Collecting AE and SAE Information

Adverse events will be collected from after the participant received the first dose of the study intervention, throughout the treatment period and including the follow-up period (Visit 5, last contact), or up until follow-up for early discontinuation.

SAEs will be recorded from the time of signing of the informed consent form.

If the investigator becomes aware of a serious adverse event with a suspected causal relationship to the investigational medicinal product that occurs after the end of the clinical study in a participant treated by him or her, the investigator shall, without undue delay, report the serious adverse event to the sponsor.

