9.4.3 Safety

Safety analyses will be performed using the safety analysis set. Adverse events will be coded using the most recent version of the Medical Dictionary for Regulatory Activities that will have been released for execution by the Sponsor/designee.

Safety data will be presented using descriptive statistics unless otherwise specified.

The AEs will be presented by system organ class and/or preferred term covering number and percentage of patients reporting at least 1 event and number of events where appropriate. An overview of AEs will present the number and percentage of patients with any AE, AEs with outcome of death, SAEs, and AEs leading to discontinuation of IP. Separate AE tables will be

provided taken into consideration relationship as assessed by the Investigator, intensity, seriousness, death, and events leading to discontinuation of IP. An additional table will present number and percentage of patients with the most common AEs.

Vital signs

Vital sign parameters will be presented for each treatment group. Summary statistics for continuous variables cover n, mean, SD, Min, Q1, median, Q3, and Max.

Details of vital sign analyses will be provided in the SAP.

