3.6.2.2 Presentation

The AEs will be presented by SOC and/or preferred term covering number and percentage of participants reporting at least 1 event and number of events where appropriate. An overview of AEs will present the number and percentage of participants with any AE, AEs with an outcome of death, Serious adverse events (SAEs), and AEs leading to discontinuation of study intervention. Separate AE tables will be provided taking into consideration the relationship to study intervention as assessed by the Investigator, intensity, seriousness, death, and events leading to discontinuation of study intervention.

AE summaries will be ordered by the international order for SOC and by decreasing frequency for preferred term within SOC.

All reported AEs will be listed along with the date of onset, date of resolution (if AE is resolved), Investigator's assessment of intensity, whether the AE is serious or not, outcome, action taken with study intervention, and possible relationship to study intervention. A by-participant listing of all AE (including AEs before first dose of study intervention) will be provided. This listing will include the following information: study period, verbatim term, MedDRA SOC and preferred term, start date/time, end date/time, time from last dose, intensity, causality, action taken, whether the AE was classified as serious, the outcome of

the AE and the concomitant or additional treatment given, if any. Any AE occurring before the first dose of study intervention and/or the AE assessments that are unresolved at the participant's last assessment in the study will be included in the data listings but will not be included in the summary tables of AEs.

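### SAP 3.6.2.1 merges repeat occurrences of an adverse event into one, which conflicts with the event counts that SAP 3.6.2.2 and protocol 9.4.3 promise

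*SAP*

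**What the plan says.** SAP 3.6.2.1 sets the counting rule and, in the same sentence, the dates of the single resulting event. An AE that one person has more than once "will only be counted once overall considering start date as the first day of first occurrence and stop date the last day"; the stop date comes from the final episode. Nothing in the sentence restricts it to one kind of table. The next two paragraphs take the maximum intensity and the worst causality for each participant.

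SAP 3.6.2.2 describes the tables by system organ class or preferred term. They are to show the "number and percentage of participants reporting at least 1 event and number of events where appropriate". Protocol 9.4.3 has the same pair of statistics: the number and percentage "of patients reporting at least 1 event and number of events where appropriate".

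Three further provisions bear on the dates:

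- SAP 3.6.2.1 treats as treatment emergent "AEs with date of onset on or after the earliest first dose of any of the components of the combination".
- SAP 3.6.2.2 lists, but does not summarise, "Any AE occurring before the first dose of study intervention".
- AEs in general are collected from the first dose, but protocol 8.4.1 adds that "SAEs will be recorded from the time of signing of the informed consent form".

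SAP 3.6.2.2 also requires listings of all reported AEs with their onset and resolution dates. The visible text of the SAP addendum does not change the AE rules.

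**The concern.** Counting a participant once per preferred term is the usual convention for incidence. This rule goes further, because it also defines a merged start and stop date, and so a merged record. A pure incidence rule would need no dates.

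The immediate loss is the event count. It is the only planned AE summary that separates one episode in each of several participants from repeated episodes in the same participants. Recurrence is plausible here: protocol 6.1.1 schedules three injections, at weeks 0, 4 and 8, and protocol 8.4.5 records upper and lower respiratory tract infections as AEs. A reaction under the same term after each of three doses would be reported as one event.

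The second, much smaller, matter is that treatment emergence depends on the onset date. If a merged record takes its onset from an occurrence before dosing, a later on-treatment occurrence could be classified with it and left out of the summary tables.

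**Working it through.** The plan states no figure to reproduce. The check applies the written rule to assumed episodes and compares it with counting each occurrence. I read an AE in the counting rule as a preferred term, the level used in the neighbouring intensity rule. Study day 1 is the day of first dose and there is no day 0.

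**1. Event count for one term**

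Let k be the number of participants with the term and m their mean number of episodes.

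- Events under the rule = k
- Events that occurred = k × m
- Undercount = 1 − k/(k × m) = 1 − 1/m

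The undercount does not depend on k. With k = 4 for illustration:

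| m (assumed) | Events under the rule | Events that occurred | Undercount |
|---|---|---|---|
| 1 | 4 | 4 | 0% |
| 1.5 | 4 | 6 | 33% |
| 2 | 4 | 8 | 50% |
| 3 | 4 | 12 | 67% |

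The participant count is 4 in every row, so the rule leaves n (%) correct and makes the event column a copy of it.

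**2. One participant, all episodes after dosing**

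Assume episodes on days 3–4, 40–41 and 80–82. Counted separately there are 3 events, all treatment emergent. Under the rule there is 1 event with onset on day 3, also treatment emergent. The participant is counted once either way, and day 3 is the correct time to first onset.

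**3. One participant, first episode before dosing**

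Only an SAE can enter this case by design, since other AEs are collected from the first dose. Assume an SAE on days −10 to −8 that recurs on days 30–32. The result depends on the order of two steps:

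| Order of steps | Onset used for the test | Treatment-emergent events | Participant in the summary table |
|---|---|---|---|
| Merge, then test onset against first dose | Day −10 | 0 | No |
| Test each occurrence, then merge | Day 30 for the recurrence | 1 | Yes |

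The SAP does not say which step comes first.

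The window for such an SAE is limited. Protocol section 4.1 allows up to 30 days from consent to screening and up to 21 days from screening to Visit 1, so at most 30 + 21 = 51 days without rescheduling. Protocol 8.3.1 also discontinues participants hospitalised for asthma or a respiratory tract infection.

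**The case against.** The best defence is that the sentence is an ordinary incidence convention, loosely worded. It stands next to the maximum-intensity and worst-causality rules, which are participant-level conventions. The listings in SAP 3.6.2.2 need each reported AE with its own dates, so unmerged records must still exist. Event counts are promised only where appropriate, the AE overview is entirely participant-level, and this is a single-arm descriptive safety analysis with no between-group comparison.

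Much of this stands, and it limits the consequence. It does not remove the conflict. The sentence states no restriction to incidence, and it prescribes dates that incidence does not need. A programmer following it would produce event counts equal to participant counts.

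A reader might infer more than the documents support:

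- **That reported durations are wrong.** In the second example the merged interval runs 82 − 3 + 1 = 80 days against 2 + 2 + 3 = 7 event-days. But neither document plans a summary of AE duration, and the listings are to carry the reported dates. The merged interval appears in no specified summary table.
- **That time to onset is wrong in general.** It is among the AE assessments in protocol Table 2. For any AE that first occurs after dosing, the start of the first occurrence is the correct time to first onset. Only the pre-dose case could distort it.
- **That on-treatment events will routinely drop out of the tables.** This needs an SAE between consent and first dose, a participant who is still dosed, recurrence of the same term, and merging before treatment emergence is assigned.
- **That the effect can be scaled to about 38 treated participants.** Protocol section 1.1 gives 38 as the estimate enrolled, meaning consented. It is not the number treated.

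**Conclusion.** The rule is wrong as written, in a limited way. SAP 3.6.2.1 cannot be applied literally and still deliver the event counts in SAP 3.6.2.2 and protocol 9.4.3. For each term the event count would equal the participant count and every repeat episode would be lost.

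The size cannot be fixed from the documents, which give no recurrence rate. It is zero if no AE recurs and 1 − 1/m otherwise: 33% to 67% for an assumed mean of 1.5 to 3 episodes per affected participant. Participant n (%) stays correct outside the pre-dose case. That case is possible but narrow, and it depends on an order of steps that the SAP does not state.

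The conclusion rests on reading the sentence as it stands, at preferred-term level. If the sponsor meant it for incidence only, the intent is sound and the wording still needs correcting.

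**What to change.** Replace the sentence in SAP 3.6.2.1 with a rule to this effect: in participant-level summaries (n, %), a participant is counted once per preferred term; for the number of events, each recorded occurrence is a separate event and keeps its own start and stop dates; treatment emergence is assigned to each occurrence before any summary is made.

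No change to SAP 3.6.2.2 or the protocol is needed. The cost is one sentence of SAP text and a check of the AE table programs. No further data are required, because occurrences are already to be listed with their dates. Section 2.12 of the SAP addendum offers a precedent: it corrected the vital-signs output because the SAP had departed from the protocol.

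### Two of the four AE partial-date rules (only month missing, only year missing) can place a post-dose non-serious AE before the first dose, and so outside the AE summary tables

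*SAP*

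**What the plan says.** **Collection.** Protocol 8.4.1: "Adverse events will be collected from after the participant received the first dose of the study intervention". SAP 3.6.2.1 agrees: "AEs are collected from the time of first dose of IP, throughout the treatment period and until Week 15 safety follow-up period is completed". Serious events start earlier (Protocol 8.4.1): "SAEs will be recorded from the time of signing of the informed consent form".

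**Classification.** SAP 3.6.2.1 decides treatment-emergent status by onset: "AEs with date of onset on or after the earliest first dose of any of the components of the combination should be considered to be" treatment-emergent. Under SAP 3.6.2.2, "Any AE occurring before the first dose of study intervention" goes into the data listings but is left out of the AE summary tables.

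**Partial start dates (SAP 3.6.2.1).** There are four patterns:

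- Only the day missing, in a dosing month: "then the day will be imputed with the first day on which study intervention was administered in that month".
- Only the month missing, in a dosing year: "then the month will be imputed with the first month in which study intervention was administered".
- Day and month missing, in a dosing year: the day and month of dosing are used.
- Only the year missing: "If only the year is missing, then the year will be imputed with the year of dosing".

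The first three have a fallback if the imputed start falls after the AE end date, and that fallback moves the start earlier. The year rule has no check at all. None of the four is compared with the first-dose date.

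**Completely unknown start date (same section).** The date of dosing is used, unless the end date is known and precedes dosing.

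**SAP Addendum.** Sections 2.3 and 2.5 add partial-date rules for OCS dependency and last exacerbation. The AE rules are unchanged.

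**The concern.** The month rule joins a recorded day to the first dosing month without asking whether that day comes before the first dose. The year rule inserts a dosing year without saying which one, although three doses over eight weeks can fall in two calendar years. For a non-serious AE, a pre-dose start contradicts the collection rule, so it can only be an artefact of imputation.

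The treatment of missing information is also inconsistent. An AE with no start date at all defaults to the dosing date and is counted. An AE with its day and year recorded can be given a pre-dose date and left out of the tables. More information gives the worse result.

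What is at stake is reported AE incidence in a small single-arm study. With an estimated 38 enrolled (Protocol synopsis), one participant is 1/38 = 2.6 percentage points if all are dosed. A participant's only event of a given term could be lost in this way.

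**Working it through.** The documents give no figure on this point, so there is none to reproduce. The check applies the rules as written.

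**Inputs**

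- Doses on days 0, 28 and 56 (Protocol 6.1.1: three doses, four weeks apart).
- AE collection from first dose to Week 15, that is 15 × 7 = 105 days (SAP 3.6.2.1).
- Assumption, not in the documents: first dose equally likely on each of 365 days (2023 was used), and onset equally likely on each of days 0 to 105.

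**Worked cases**

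1. *Month missing.* First dose 20 March 2023; AE recorded as day 10, month unknown, 2023. True onset may be 10 April, 10 May or 10 June. The rule gives 10 March 2023, 10 days before the first dose.
2. *Year missing.* First dose 10 November 2022, later doses 8 December 2022 and 5 January 2023; AE recorded as 15 February, year unknown. True onset is 15 February 2023. With the first-dose year the rule gives 15 February 2022, about nine months before the first dose. With the last-dose year it gives the correct date.

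**Enumeration.** 365 first-dose dates × 106 onset days = 38,690 post-dose onsets.

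| Missing part | Placed before first dose | Share |
|---|---|---|
| Day only | 0 | 0% |
| Day and month | 0 | 0% |
| Month only | 14,187 | 14,187/38,690 = 36.7% |
| Year only, first-dose year | 5,519 | 5,519/38,690 = 14.3% |
| Year only, last-dose year | 1,225 | 1,225/38,690 = 3.2% |

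The zero for day and month reads the dosing date as the first dose in the recorded year. The counts were identical whether the AE ended the same day, ended five days later or was ongoing, so the end-date fallback does not repair the problem. Month-only cases are placed up to 30 days too early. A further 363 to 388 of the 38,690 month-only cases give a date that does not exist, such as day 31 in a 30-day month.

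**Year counts by hand**

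- *First-dose year.* An onset on day *o* falls in the next calendar year for exactly *o* of the 365 first-dose dates. The total is 0 + 1 + … + 105 = 105 × 106/2 = 5,565. Of these, 46 fall on 29 February 2024, which has no counterpart in 2023, leaving 5,565 − 46 = 5,519.
- *Last-dose year.* The error needs onset after New Year but the last dose (day 56) before it. If the first dose is *r* days before 1 January, *r* runs from 57 to 105, and each *r* gives 106 − *r* onsets. The total is 49 + 48 + … + 1 = 49 × 50/2 = 1,225.

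**The case against.** **The exclusion is inferred.** SAP 3.6.2.2 does not say that the imputed date decides whether an AE precedes the first dose, and a programmer who knows the collection rule might treat every non-serious AE as post-dose. This stands as a limit. But the SAP names no other date to use, and 3.6.2.1 defines treatment-emergence by onset date. The events are not lost altogether, because they remain in the listings.

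**The gaps are probably rare.** AEs are asked about at each visit, and there are data queries and ongoing source data verification. A known day with an unknown month, or a known day and month with an unknown year, is an unusual record. This stands too: the percentages are shares of such records, not expected trial rates.

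**Stronger readings that the documents do not support**

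- *That the error can only lower AE counts.* SAEs are recorded from consent, so genuine pre-dose SAEs can exist and can be moved the other way. With a first dose on 20 March, an ongoing SAE with true onset 25 February and the month missing is imputed to 25 March and counted as treatment-emergent.
- *That the rules breach a stated conservative principle for missing AE data.* The conservative approach in SAP 3.6.2.1 covers missing severity and causality, not dates. The real inconsistency is with the rule for completely unknown start dates.
- *That a blanket floor at first dose would be a safe repair.* Take an SAE recorded in February with the day missing, ending 25 March, with a first dose on 20 March. It is known to be pre-dose, and the present day rule correctly gives 1 February. A floor would move it to 20 March and make it treatment-emergent.

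**Conclusion.** The point holds, narrowly. Two stated rules can give an impossible pre-dose start to a non-serious AE, and nothing in the SAP or Addendum catches it. Under uniform first-dose and onset dates, about 37% of AEs with only the month missing are affected. For AEs with only the year missing it is 3% to 14%, and that range exists because the SAP does not define which dosing year applies. For SAEs the same rules can misclassify in either direction.

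The effect on the reported tables cannot be sized, because the documents do not give the number of such records; it is likely to be small. The consequence rests on the imputed date being used to classify the event. This is a minor correction, worth making because it is cheap.

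**What to change.** Amend SAP 3.6.2.1, or add to the Addendum, for non-serious AEs with only the month or only the year missing:

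- Impute the earliest date that agrees with the recorded date parts, falls on or after the first dose and is not after the AE end date.
- If no such date exists, query the record. Count the AE as treatment-emergent unless the recorded parts or the end date show onset before the first dose.
- For SAEs, do not move an onset that the recorded parts place before the first dose.

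Applied to the worked cases, this gives 10 April 2023 and 15 February 2023, both post-dose and consistent with what was recorded. By construction it places none of the 38,690 enumerated onsets before the first dose. Searching for a date that agrees with the recorded parts also removes the non-existent dates.

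Defining the dosing year as the last-dose year would not be enough: 3.2% of year-only cases would still be placed before the first dose. The day-only and day-and-month rules need no change for this purpose.

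The cost is a few sentences in the SAP, a small change to the AE date derivation and perhaps a few data queries. Data collection, endpoints and trial conduct are unaffected.
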